10.3.3. Categorical Variables

A shift table from baseline to applicable analysis visits will be provided for the categorical variables including PPSI score, PGA score for palms and soles, and subject's assessment for PPP Sign/Finding using PPSI score.

10.4. Subgroup Analysis

Subgroup analyses for comparisons of subjects achieving PPPASI-50 at Week 16 between apremilast 30 mg BID and placebo, based upon following classification variables will be provided to determine whether the treatment effect is consistent across various subgroups. The categorical groups of each subgroup may be pooled based on the number of observations available.

- Age category (< 40, \geq 40 to < 65, \geq 65 to < 75, \geq 75)
- Sex (Male, Female)
- BMI category (< 25, \geq 25 to < 30, \geq 30)
- Tobacco Use (Current/Past User, Non-User)
- Duration of PPP category (< 2, \geq 2 to < 6, \geq 6 to < 10, \geq 10 years)
- PPPASI score range at randomization from clinical data (\leq 20, \geq 21 to \leq 30, \geq 31)
- Presence of focal infection at randomization from clinical data (Yes, No)
- History of focal infection (Yes, No)
- Presence of pustulotic arthro-osteitis (PAO) (Yes, No)
- Prior Disease-modifying antirheumatic drugs (DMARDs) (Yes, No)

The consistency of the treatment effect will be assessed in the context of the primary efficacy analysis model with terms for treatment, stratum, and the covariate. Treatment effects and nominal 95% confidence intervals by category for the classification variables listed above will be provided. Formal statistical testing of these interactions will not be performed.

CC-10004 (Apremilast)

Statistical Analysis Plan. Protocol CC-10004-PPP-001

11. SAFETY ANALYSIS

Safety analyses will be performed using the safety population. The safety analyses for the placebo-controlled phase will be based on the safety population and presented by treatment group, and the safety analyses for the apremilast-exposure period will be based on the apremilast subjects as treated population and presented by treatment group (Placebo/30 mg BID, 30 mg BID as initiated and 30 mg BID as treated).

For safety analyses in the placebo-controlled phase, baseline will be relative to the first dose date following randomization at Week 0. For safety analyses in apremilast-exposure period, baseline will be relative to the first apremilast dose date at Week 0 for subjects initially randomized to apremilast or Week 16 for subjects initially randomized to placebo and switched to apremilast in the active treatment phase (Weeks 16 to 32).

Unless otherwise specified, the analyses of AEs and marked abnormalities (laboratory parameters and vital signs) for both the placebo-controlled phase and apremilast-exposure period will include the subject incidence rate. To account for the different exposure to the IP, the exposure-adjusted incidence rate will also be presented.

- Subject incidence: Subject incidence (i.e., percentage [%] used in a frequency summary) is defined as the number of subjects with the specific event divided by the number of subjects included in the analysis. Subjects with multiple occurrences of the specific event in the specific phase or analysis period will be counted only once in the numerator. If a subject experiences multiple AEs under the same preferred term (system organ class), then the subject will be counted only once for that preferred term (system organ class).
- Exposure-adjusted incidence rate (EAIR) per 100 subject-years: The EAIR per 100 subject-years is defined as 100 times the number of subjects with the specific event divided by the total exposure time (in years) among subjects included in the analysis. Subjects with multiple occurrences of the specific event in the specific phase or analysis period will be counted only once in the numerator. The exposure time for a subject without the specific event is the treatment duration, whereas the exposure time for a subject with the specific event is the treatment duration up to the start date (inclusive) of the first occurrence of the specific event. The total exposure time in years is calculated by dividing the sum of exposure time in days over all subjects included in the analysis by 365.25. The EAIR per 100 subject-years is interpreted as the expected number of subjects with at least one occurrence of the specific event per 100 subject-years of exposure to IP.

For safety analysis, no inferential testing for statistical significance will be performed.

Individual subject listings will be provided for all safety data obtained.

As necessity requires, additional safety information may be provided.

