5.2.1. Analysis Periods

Per protocol specification, data summary and analysis will be provided for the following periods, if appropriate.

- Placebo-controlled Phase/Period

This period starts on the day of randomization (Week 0/Visit 2), and stops on below, whichever is later:

- (1) the day of Week 16/Visit 10 if the subject continued study treatment to the active treatment phase
- (2) the day of the discontinuation if the subject discontinued study treatment prior to or at Week 16/Visit 10
- (3) the last known study day if the subject is lost to follow-up prior to Week 16/Visit 10

CC-10004 (Apremilast)

Statistical Analysis Plan. Protocol CC-10004-PPP-001

The two treatment arms are apremilast 30 mg BID or Placebo.

- Active Treatment Phase/Period

This period starts on one day after the day of the first dose of apremilast at Week 16/Visit 10, and stops on either below.

- (1) the day of Week 32/Visit 14
- (2) the day of the discontinuation if the subject discontinued prior to or at Week 32/Visit 14
- (3) the last known study day if the subject lost to follow-up prior to Week 32/Visit 14 during the phase

The two treatment arms are 30 mg BID/30 mg BID, and Placebo/30 mg BID.

For safety analysis, the period starts on the day of the first dose of apremilast in the period.

- Observational Follow-up Phase/Period

Subjects who complete or discontinue the study treatment, will be followed up for 28 days after last dose of IP.

For adverse event analysis, data from the first 28 days after the last dose of IP will be included in the precedent treatment phase and data after the 28 days will be presented separately.

- Apremilast-exposure Period

This period starts on the date of either:

- (1) the first dose of IP following randomization (Week 0/Visit 2) for subject who are treated with apremilast from Week 0
- (2) the first dose of IP from the IP dispensed at Week16/Visit 10 for subjects who were originally treated with placebo and are switched to apremilast at Week 16

This period stops on either: (1) data restriction date; or (2) the end of the study.

During the apremilast-exposure period, data are presented by treatment sequence, i.e., Placebo/30 mg BID, 30 mg BID as Initiated, and a total column of 30 mg BID as Treated.

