9.1. Treatment Duration

Treatment duration will be descriptively summarized. Treatment duration (in weeks) is calculated as (the date of the last dose of IP – the date of the first dose of IP + 1) / 7. Imputation rule for partially or completely missing last dose date is specified in [Section 17.2.4](#). Summary statistics for treatment duration (in weeks), as well as a frequency summary of treatment duration categories (placebo-controlled phase: < 4, ≥ 4 to < 8, ≥ 8 to < 12, ≥ 12 to < 16, ≥ 16, active treatment phase: ≥ 16 to < 20, ≥ 20 to < 24, ≥ 24 to < 28, ≥ 28 to < 32, ≥ 32 weeks) will be provided.

Treatment duration for apremilast-exposure period is calculated from the date of the first apremilast administered, which is the date of the first administration of apremilast on/after the randomization at Week 0/Visit 2 or switched to apremilast at Week 16/Visit 10, to the last apremilast administered date for subjects who discontinue in the first 32 weeks or who complete the study at Week 32/Visit 14. Imputation rule for partially or completely missing last dose date is specified in [Section 17.2.4](#).

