11.1. Adverse Events

Adverse events will be analyzed in terms of treatment-emergent adverse events (TEAEs) which are defined as any AEs that begin or worsen on or after the first dose of IP through 28 days after the last dose of IP or study treatment discontinuation date, whichever is later. All AEs will be classified using the Medical Dictionary for Regulatory Activities (MedDRA) classification

CC-10004 (Apremilast)

Statistical Analysis Plan. Protocol CC-10004-PPP-001

system version 21.1 or higher. Unless otherwise specified, AEs will be summarized by system organ class (SOC) and preferred term (PT), with SOCs presented in the standard international order and PTs within SOCs will be presented in descending order of subject incidence.

A treatment-related TEAE is defined as TEAE which was suspected to be related to the study drugs.

AEs and marked abnormalities will be summarized by subject incidence and EAIR for the placebo-controlled phase (Weeks 0 to 16) and for the Apremilast-exposure period. In addition, selected summaries for the active treatment phase (Weeks 16 to 32) and the observational follow-up phase (4 weeks) will be presented.

An overall summary of the following AE categories will be provided.

- TEAE
- TEAE related to study drug
- Severe TEAE
- Serious TEAE
- Serious TEAE Related to Study Drug
- TEAE leading to dose reduction
- TEAE leading to drug interruption
- TEAE leading to drug withdrawal
- TEAE leading to death

In addition, for apremilast-exposure period overall summary of TEAEs will also be provided.

Tables summarizing the incidence of TEAEs by SOP and/or PT will be generated for each of the following:

- All TEAEs
- Most frequent TEAEs (subject incidence $\geq 5\%$ or another cut-off if justified)
- Treatment-related TEAEs
- TEAEs by maximum severity
- Serious TEAEs and treatment-related serious TEAEs
- TEAE leading to dose reduction
- TEAE leading to drug interruption
- TEAE leading to drug withdrawal
- TEAE leading to death
- First onset and new events of TEAE by exposure interval
 - placebo controlled phase (weeks): ≤ 1 , > 1 to ≤ 2 , > 2 to ≤ 4 , > 4 to ≤ 8 , > 8 to ≤ 12 , > 12 to ≤ 16 , > 16

CC-10004 (Apremilast)

Statistical Analysis Plan. Protocol CC-10004-PPP-001

- apremilast-exposure period (weeks): ≤ 1 , > 1 to ≤ 2 , > 2 to ≤ 4 , > 4 to ≤ 8 , > 8 to ≤ 12 , > 12 to ≤ 16 , > 16 to ≤ 24 , > 24 to ≤ 32 , > 32
- TEAE for the subgroups in [Section 10.4](#)

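### The exposure-adjusted incidence rate counts adverse events for 28 days after the last dose but stops the clock at the last dose, mainly distorting the apremilast-exposure tables

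*SAP*

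**What the plan says.** **Numerator.** SAP 11.1 analyses adverse events as treatment-emergent events (TEAEs). Their window opens at the first dose and runs "through 28 days after the last dose of IP or study treatment discontinuation date, whichever is later". SAP 5.2.1 assigns the follow-up time to a phase: "data from the first 28 days after the last dose of IP will be included in the precedent treatment phase".

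**Denominator.** SAP 11 states: "The exposure time for a subject without the specific event is the treatment duration". A subject with the event contributes "the treatment duration up to the start date (inclusive) of the first occurrence of the specific event". SAP 9.1 defines the duration in days, before conversion to weeks, as "calculated as (the date of the last dose of IP – the date of the first dose of IP + 1"). For the apremilast-exposure period it runs "to the last apremilast administered date for subjects who discontinue in the first 32 weeks or who complete the study at Week 32/Visit 14". The period itself ends elsewhere: "This period stops on either: (1) data restriction date; or (2) the end of the study".

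**Use.** SAP 11 presents the EAIR beside simple subject incidence, as the adjustment for unequal exposure, and interprets it per 100 subject-years on product. SAP 5.2.1 and 11 lay out the apremilast-exposure tables in three columns: Placebo/30 mg BID, 30 mg BID as Initiated, and the two pooled as 30 mg BID as Treated.

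**The concern.** Take two subjects who stop treatment on the same day. One has a first event 20 days later, and it is counted. The other is observed through the same 20 days without an event and contributes none of them. Protocol 6.3 and 10.1 follow everyone for adverse events for 28 days after the last dose, so this time is at risk and is observed, but the rate leaves it out.

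The omitted time is fixed at 28 days, so its weight depends on how long a subject was treated. A statistic introduced to remove the effect of unequal exposure therefore carries an error that varies with exposure. The place to worry is the apremilast-exposure period, where a group with about 16 planned weeks on drug stands next to one with about 32.

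The mismatch also reaches the exposure-interval tables in SAP 11.1. A first event in follow-up can fall in the last interval (beyond Week 32, or beyond Week 16 in the placebo-controlled phase). The denominator there includes only subjects whose treatment duration exceeds the lower bound, so such a cell may hold events with little or no denominator.

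**Working it through.** The documents give no EAIR, event rate or dropout rate, so there is no stated figure to reproduce. The check compares the planned rate with one whose numerator and denominator both run through last dose + 28 days.

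**Inputs**
- Time on apremilast at full planned exposure, T: 112 days for Placebo/30 mg BID (16 weeks) and 224 days for 30 mg BID as Initiated (32 weeks), from SAP 5.2.
- Post-dose window: 28 days (SAP 5.2.1, 11.1).
- Group size: 43 per arm (Protocol 4.1).

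**1. Uncommon events.** The numerators are identical, so planned/matched is a ratio of person-time, (T + 28)/T:
- Placebo/30 mg BID: 140/112 = 1.25
- 30 mg BID as Initiated: 252/224 = 1.125
- Pooled, equal group sizes: (140 + 252)/(112 + 224) = 1.167
- Spurious ratio between the sequences: 1.25/1.125 = 1.11

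**2. Commoner events.** With constant hazard L per day through follow-up, planned/matched = [1 − exp(−L(T + 28))]/[1 − exp(−LT)]. At an assumed 100 per 100 subject-years, L = 1/365.25:
- T = 112: 0.3184/0.2641 = 1.206
- T = 224: 0.4984/0.4584 = 1.087

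Other assumed rates:

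| Rate per 100 subject-years | Excess, T = 112 | Excess, T = 224 |
|---|---|---|
| 5 | 24.8% | 12.3% |
| 20 | 24.1% | 11.7% |
| 100 | 20.6% | 8.7% |
| 400 | 11.0% | 2.5% |

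It is unclear what treatment duration up to the event start means when the event starts after the last dose. Counting time to that start changes the row for 100 only to 19.6% and 8.4%, because event-free subjects still lose 28 days.

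**3. Illustration.** Assume 43 subjects per group, full exposure and 5 subjects with the event, ignoring time lost after events.
- Placebo/30 mg BID: 43 × 112/365.25 = 13.19 subject-years gives 37.92 per 100 as planned; 43 × 140/365.25 = 16.48 gives 30.34 matched.
- 30 mg BID as Initiated: 43 × 224/365.25 = 26.37 gives 18.96 as planned; 43 × 252/365.25 = 29.67 gives 16.85 matched.

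**4. A different benchmark.** Compare instead with a strictly on-treatment rate. If the off-drug hazard is a fraction f of the on-drug hazard, the excess for uncommon events is f × 28/T. For f = 1 this is 25% and 12.5%; for f = 0.5 it is 12.5% and 6.25%; for f = 0 it is zero.

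**5. Placebo-controlled phase.** Subjects who continue into the active phase have no post-dose window here. If a proportion d stop mid-phase (56 days, assumed), the excess for uncommon events is 28d/[112(1 − d) + 56d]:
- d = 5%: 1.4/109.2 = 1.3%
- d = 15%: 4.2/103.6 = 4.1%

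Even with 5% in one arm and 15% in the other, the between-arm distortion is 1.041/1.013, about 1.03.

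**The case against.** The strongest reply is that little rests on this rate. Safety is descriptive, with no inferential testing, and subject incidence, interval tables and listings are all provided. That stands: no error rate, success rule or stopping rule is affected.

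Three stronger readings are tempting, and the documents do not support them.

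- **That the randomised safety comparison is biased against the arm with more discontinuations.** Step 5 shows a small effect, and it differs between arms only if discontinuation differs. Neither document gives a dropout rate.
- **That every rate is inflated by 12.5% to 25%.** Those figures are limits for uncommon events against a matched rate. Against an on-treatment rate the excess vanishes if no first event starts after the last dose. Protocol 6.5.5 reports that severe gastrointestinal events arose mostly early in treatment, so for such events the off-drug hazard may well be lower.
- **That matching the windows would make the two sequences comparable.** It would not if onset is early. Suppose 10% of subjects have the event, at Week 2 on average. Mean time per subject as planned is 0.9 × 16 + 0.2 = 14.6 weeks against 0.9 × 32 + 0.2 = 29.0, so the rate ratio is 2.0. With matched windows it is 32.6/18.2, or 1.8. Unequal follow-up dominates; the mismatch is a second, avoidable error.

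It can also be said that the SAP defines its ratio openly. But the definition does not give the meaning that SAP 11 attaches to it, because the numerator includes events arising after exposure ended.

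**Conclusion.** The rule is wrong as written and should be corrected, though no trial conclusion depends on it. The direction does not rest on the hazard assumption: against a matched rate the planned EAIR has the same numerator over less time, and against an on-treatment rate it has an equal or larger numerator over essentially the same time.

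Against a matched rate, the excess in the apremilast-exposure period is up to 25% for Placebo/30 mg BID and up to 12.5% for 30 mg BID as Initiated, or about 21% and 9% at 100 per 100 subject-years with constant hazard. The spurious ratio between them is up to about 1.11. These limits assume full planned exposure and complete 28-day follow-up; early stopping shortens mean exposure and raises the ratio. In the placebo-controlled phase the effect is about 1% to 4% under the assumed 5% to 15% discontinuation.

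**What to change.** Adopt one of two definitions in SAP 11 and state it.

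**(a) Match the clock to the event window.** For a subject without the event, count from first dose to the earliest of:
- the end of that subject's TEAE window (last dose + 28 days, or the discontinuation date if later);
- last contact;
- the data cut-off;
- for the placebo-controlled phase, in subjects who continue, the start of active-phase dosing.

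For a subject with the event, count to its start date. Label the unit as subject-years at risk. Do not cap at the phase end date for early discontinuers: SAP 5.2.1 ends their placebo-controlled phase at discontinuation, so that cap would recreate the mismatch.

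**(b) Match the events to the clock.** Keep treatment duration as the denominator and restrict the EAIR numerator to events starting on or before the last dose.

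Apply the same choice to the exposure-interval tables in SAP 11.1.

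**Cost.** No new data are needed: one definition and one derived variable or event flag change, and the interval tables follow. Under (a), stated rates fall by up to 1 − 112/140 = 20% for Placebo/30 mg BID and 1 − 224/252 = 11% for 30 mg BID as Initiated (uncommon events, full planned exposure), and the denominator includes off-drug time, which dilutes rates of early-onset events. Under (b), post-dose events appear only in subject incidence and listings.

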11.1. Adverse Events

Adverse events will be analyzed in terms of treatment-emergent adverse events (TEAEs) which are defined as any AEs that begin or worsen on or after the first dose of IP through 28 days after the last dose of IP or study treatment discontinuation date, whichever is later. All AEs will be classified using the Medical Dictionary for Regulatory Activities (MedDRA) classification

CC-10004 (Apremilast)

Statistical Analysis Plan. Protocol CC-10004-PPP-001

system version 21.1 or higher. Unless otherwise specified, AEs will be summarized by system organ class (SOC) and preferred term (PT), with SOCs presented in the standard international order and PTs within SOCs will be presented in descending order of subject incidence.

A treatment-related TEAE is defined as TEAE which was suspected to be related to the study drugs.

AEs and marked abnormalities will be summarized by subject incidence and EAIR for the placebo-controlled phase (Weeks 0 to 16) and for the Apremilast-exposure period. In addition, selected summaries for the active treatment phase (Weeks 16 to 32) and the observational follow-up phase (4 weeks) will be presented.

An overall summary of the following AE categories will be provided.

- TEAE
- TEAE related to study drug
- Severe TEAE
- Serious TEAE
- Serious TEAE Related to Study Drug
- TEAE leading to dose reduction
- TEAE leading to drug interruption
- TEAE leading to drug withdrawal
- TEAE leading to death

In addition, for apremilast-exposure period overall summary of TEAEs will also be provided.

Tables summarizing the incidence of TEAEs by SOP and/or PT will be generated for each of the following:

- All TEAEs
- Most frequent TEAEs (subject incidence $\geq 5\%$ or another cut-off if justified)
- Treatment-related TEAEs
- TEAEs by maximum severity
- Serious TEAEs and treatment-related serious TEAEs
- TEAE leading to dose reduction
- TEAE leading to drug interruption
- TEAE leading to drug withdrawal
- TEAE leading to death
- First onset and new events of TEAE by exposure interval
 - placebo controlled phase (weeks): ≤ 1 , > 1 to ≤ 2 , > 2 to ≤ 4 , > 4 to ≤ 8 , > 8 to ≤ 12 , > 12 to ≤ 16 , > 16

CC-10004 (Apremilast)

Statistical Analysis Plan. Protocol CC-10004-PPP-001

- apremilast-exposure period (weeks): ≤ 1 , > 1 to ≤ 2 , > 2 to ≤ 4 , > 4 to ≤ 8 , > 8 to ≤ 12 , > 12 to ≤ 16 , > 16 to ≤ 24 , > 24 to ≤ 32 , > 32
- TEAE for the subgroups in [Section 10.4](#)

For the summary of the new events of TEAE by exposure interval, each subject is counted once for either subject incidence or EAIR for each applicable specific TEAE in each exposure interval where an event started. The denominator of a subject incidence is the number of subjects with treatment duration exceeding the lower bound of the particular exposure interval, while the denominator of an EAIR is the sum of the exposure time during the exposure interval (up to the first event start date for subjects with at least one event starting in the interval) among the same number of subjects as in the denominator of the corresponding subject incidence. For the summary of the first onset of TEAE by exposure interval, only the first onset of specific TEAE is considered for each subject.

Listings for the corresponding summary tables will be presented separately. A listing including non-treatment-emergent AEs will be provided.

11.2. Adverse Events of Special Interest

The following TEAEs of special interest will be summarized:

- Depression: MedDRA narrow scope sub-SMQ of Depression (excluding suicide and self-injury)
- Serious infection: MedDRA primary PTs from the SOC of Infections and infestations. Only the events that were assessed as serious
- Risk of Triggering Suicide: MedDRA narrow scope SMQ of Suicide/self-injury

The following summaries will be provided for TEAEs included in the above-mentioned AEs of interest:

- All TEAEs;
- Severe TEAEs;
- Serious TEAEs;
- TEAEs leading to treatment discontinuation;
- TEAEs leading to dose reduction/interruption;
- TEAEs leading to death.

11.3. Clinical Laboratory Evaluations

The endpoints for clinical laboratory evaluations include:

- Laboratory marked abnormalities
- Observed value and change from baseline over time in the following selected laboratory parameters
 - Hematology: platelets, hemoglobin, leukocytes, neutrophils, segmented, lymphocytes

CC-10004 (Apremilast)

Statistical Analysis Plan. Protocol CC-10004-PPP-001

- Serum chemistry: hemoglobin A1C, magnesium, sodium, potassium, total bilirubin, glucose, lactate dehydrogenase, calcium, albumin, creatinine, alanine aminotransferase, alkaline phosphatase, aspartate aminotransferase, blood urea nitrogen, urate, phosphate, triglycerides, cholesterol
- Shifts from baseline to post-baseline time points and to the worst post-baseline value in terms of normal/abnormal (low and/or high) in the above hematology and serum chemistry parameters

Summary statistics of observed values and changes from baseline in laboratory parameters will be provided over time. Frequency summaries (shift tables) of shifts from baseline to post-baseline time points and to the worst post-baseline value in terms of normal/abnormal will be provided.

Laboratory marked abnormalities will be summarized; subject incidence and EAIR for each abnormality will be calculated based on subjects with a baseline value and at least one post-baseline value. Laboratory marked abnormalities will also be summarized for subjects with normal values at baseline and for subjects with abnormal values at baseline separately. For the purposes of these summaries, subjects with abnormal (normal) values at baseline are defined as those whose baseline value is low (not low) for criteria concerning low values and those whose baseline value is high (not high) for criteria concerning high values; both low and high are relative to the laboratory normal range.

Individual subject data of all laboratory data including urinalysis will be listed and values outside of the standard reference range will be flagged.

